4.9. Pharmacodynamic and Biomarkers Variables

Pharmacodynamic and biomarker variables are:

- Serum total IgE
- Serum peanut-specific antibody assays (IgE, IgG, IgG4 against peanut extract and peanut protein allergen components)
- Fractional Exhaled Nitric Oxide (FeNO)
- Basophil Sensitivity Test (optional)
- Peanut-reactive Th2A cells (optional)

Biomarker samples will be collected at time points according to according to Section 10.2.

4.10. Pediatric Eosinophilic Esophagitis Symptom Score Questionnaire

The Pediatric Eosinophilic Esophagitis (EoE) Symptom Score PEESS v2.0 measures subjectrelevant outcomes. The PEESS v2.0 holds promise for being a valuable tool to follow the clinical course of EoE or an EoE-like immune-mediated GI syndrome. However, it was not designed to establish a diagnosis of EoE and has not been validated for use in subjects with GI symptoms of other etiologies. Furthermore, the discriminant validity of the questionnaire has not been reported in either longitudinal natural history or interventional studies. For these reasons, the use of the PEESS v2.0 to monitor the clinical course of GI symptoms must be considered exploratory.

Subjects that discontinue because of GI AEs will be asked to complete the PEESS v2.0 questionnaire, with the assistance of a parent or guardian, as appropriate, every month for 6 months.

CONFIDENTIAL

5. STATISTICAL METHODS

For continuous variables, descriptive statistics will include the following: the number of subjects reflected in the calculation (n), mean, standard deviation, median, first quartile (Q1), third quartile (Q3), minimum, and maximum.

For categorical or ordinal data, frequencies and percentages will be displayed for each category.

All data will be summarized by the following treatment groups in each period:

- 1. Double-blind treatment period before dosing with AR101 (4 weeks)
 - Dupilumab
 - Placebo
- 2. Double-blind treatment period with up-dosing of AR101 (24 to 36 weeks):
 - Dupilumab + AR101
 - Placebo + AR101
- 3. Double-blind maintenance period of AR101 (24 weeks):
 - Continuously on placebo+ AR101
 - Previously on dupilumab + AR101 and re-randomized to placebo + AR101 (dupilumab + AR101/placebo + AR101)
 - Continuously on dupilumab + AR101

5.1. Demographics and Baseline Characteristics

Demographics and baseline characteristics will be summarized by treatment group for mFAS, FAS and SAF. They will be summarized by treatment group for FAS-maintenance and SAF-maintenance for subjects who entered maintenance period. Listing of demographics and baseline characteristics will be presented.

5.2. Medical History

Medical history will be summarized by primary SOC and PT for each treatment group based on SAF. The table will be sorted by decreasing frequency of SOC followed by PT based on the overall incidence across treatment groups. Medical history will be listed, sorted by treatment groups based on the SAF.

Subject allergic/atopic medical history and subject family allergic/atopic medical history will be summarized and listed.

5.3. Prior and Concomitant Medications/Procedures

Number and proportion of subjects taking prior/concomitant medications, prohibited medications and rescue medications will be summarized for each treatment group and study total based on the SAF and SAF-maintenance by ATC level 2 and ATC level 4, sorted by decreasing frequency of ATC level 2 and ATC level 4 based on the overall incidence for the combined treatment groups for each study period.

CONFIDENTIAL

Page 36 of 86

Number and proportion of subjects taking prior/concomitant procedures will be summarized for each treatment group and study total based on the SAF and SAF-maintenance, sorted by decreasing frequency of SOC and PT based on the overall incidence for the combined treatment groups for each study period.

In addition, the summary of prior/concomitant medications/procedures will be performed for subjects who were impacted by COVID-19 pandemic and not impacted by COVID-19 pandemic in each study period, respectively. The summary will be performed for pre-, during, and post-COVID-19 periods for subjects impacted by COVID-19, if applicable.

Number and proportion of subjects taking at least one epinephrine and short-term use of systemic corticosteroids for treatment of acute-allergic reactions will be summarized during the following periods,

- Screening DBPCFCs of peanut protein
- Week 4 IDED
- Post up-dosing DBPCFCs of peanut protein
- Post maintenance DBPCFCs of peanut protein
- End of study DBPCFCs of peanut protein

The number of episodes of epinephrine use and short-term use of systemic corticosteroids during up-dosing period (excluding post up-dosing DBPCFCs) and during maintenance period (excluding post maintenance DBPCFCs) will be summarized, respectively.

Kaplan-Meier curves for time to first rescue treatment use will be created for each study period.

Listing of pre-treatment and concomitant medications will include generic name, ATC levels 2 and 4, indication, the study day of onset (for medications started before treatment, the study day of onset = date of medication start – date of the first dose; for medication started on or after treatment, the study day of onset = date of medication start – date of the first dose + 1), the study day of medication end date, ongoing status, dose, frequency, and route.

5.4. Subject Disposition

The following summaries by table will be provided:

- The total number of screened subjects and the screen failure reasons: met the inclusion criteria regarding the target indication and signed the informed consent form (ICF)
- The total number of randomized subjects in each study treatment period: received a randomization number from IWRS
- The total number of subjects in each analysis set
- The total number of subjects who discontinued the study and the reasons for discontinuation (including COVID-19 related reasons)
- The total number of subjects who discontinued the study in each study treatment period and the reasons for discontinuation (including COVID-19 related reasons)

- The total number of subjects who discontinued the study treatment in each study treatment period and the reasons for discontinuation (including COVID-19 related reasons)
- A summary table of protocol deviations

The following listings will be provided:

- Listing of subjects disposition including: date of randomization, date of first dupilumab/placebo injection, date of re-randomization, date of the last visit, completed study or discontinued by reason
- A listing of subjects randomized but not treated, treated but not randomized, and subjects randomized but not treated as randomized, if applicable
- A listing of subjects prematurely discontinued from the study treatment, along with reasons for discontinuation in each study period
- A listing of protocol deviations will be provided

Kaplan-Meier curve for time to withdraw from the study and from the study treatment in each study treatment period will be created, respectively.

5.5. Extent of Study Treatment Exposure

5.5.1. Measurement of Compliance

The compliance with study treatment will be calculated separately for dupilumab/placebo injection and AR101 oral home dosing for each study period as follows:

Treatment compliance of dupilumab or placebo = (Number of dupilumab/placebo injections during exposure period) / (Number of planned dupilumab/placebo injections during exposure period) x 100%;

For treatment compliance calculation of dupilumab/placebo injection, the two injections including one loading dose at the randomization visit 2 will be counted as 1 injection.

Treatment compliance of home dosing AR101 = (total actual peanut dose protein [mg] received during exposure period) / (total of planned dose peanut protein [mg] during exposure period) x 100%.

The treatment compliance will be presented by the following specific ranges for each treatment group: <80%, and $\geq80\%$.

Listing of dupilumab/placebo compliance will be presented with study drug, study drug injection date/time, study day, injection location, kit number, whether or not the total dose is administered for each dose, and compliance rate.

Listing of AR101 compliance for home dosing will be presented with AR101 dose date/time, study day, AR101 assigned dose, whether or not the full dose was taken, amount taken for partial dose, reasons for partial or missed AR101 dose.

5.5.2. Exposure to Investigational Product

The duration of exposure to Dupilumab/Placebo in day will be presented by treatment group for each study period and calculated as:

(Date of last dupilumab/placebo injection in the respective study period – date of first study drug injection) + 14 days

The duration of exposure to AR101 in day for each study period will be calculated as:

(Date of last AR101 taken in the respective study period – date of first AR101 taken) + 1 day

Note: the calculations are regardless of temporary dosing interruption.

Summary of exposure to study drug will include the number of study drug doses administered and duration of exposure. The duration of exposure to dupilumab/placebo and AR101 during the study will be summarized by treatment group using number of subjects, mean, SD, minimum, Q1, median, Q3, and maximum. These summaries will be provided for each study period separately.

In addition, the duration of exposure to study drug will be summarized categorically by counts and percentages for each of the following categories and cumulatively by these categories as well: ≥ 14 days, ≥ 28 days, ≥ 42 days, ≥ 56 days, ≥ 70 days, ≥ 84 days, ≥ 98 days, ≥ 112 days, ≥ 126 days, ≥ 140 days, ≥ 154 days, ≥ 168 days, ≥ 182 days, ≥ 196 days, ≥ 210 days, ≥ 224 days, ≥ 238 days, ≥ 252 days, ≥ 266 days, ≥ 280 days, ≥ 294 days, ≥ 308 days, ≥ 322 days, ≥ 336 days, ≥ 350 days, and ≥ 364 days.

The duration of observation period during the study in day is calculated as:

(Date of the last visit – date of the first study drug injection) +1 day.

The duration of observation period will be summarized descriptively using number of subjects, mean, SD, median, Q1, Q3, minimum and maximum. In addition, the number (%) of subjects with observation periods will be presented by specific time periods. The time periods of interest are specified as: < 15 days, \geq 15 days, \geq 29 days, \geq 43 days, \geq 57 days, \geq 71 days, \geq 85 days, \geq 99 days, \geq 113 days, \geq 127 days, \geq 141 days, \geq 155 days, \geq 169 days, \geq 183 days, \geq 197 days, \geq 225 days, \geq 239 days, \geq 267 days, \geq 281 days, \geq 295 days, \geq 309 days, \geq 323 days, \geq 337 days, \geq 351 days, \geq 365 days, \geq 379 days, \geq 393 days, \geq 407 days, \geq 421 days, \geq 435 days, and \geq 449 days.

Listing of dose administration will be presented with information on administration date/time, study day, locations of injections, kit number, and whether or not the total dose is administered for each dose will be presented.

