11.4.4.3. Treatment Exposure

The duration of exposure during the study will be presented by treatment group and calculated as:

(Date of last study drug injection – date of first study drug injection) + 14 days

The number (%) of subjects randomized and exposed to double-blind study drug will be presented by specific time periods for each treatment group. The time periods of interest will be specified in the SAP.

In addition, duration of exposure during the study will be summarized for each treatment group using number of subjects, means, standard deviation, minimums, Q1, medians, Q3, and maximums.

A summary of the number of doses by treatment group will be provided.

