2.4. Study Plan

The study consists of a screening period of up to 16 weeks, a 28 to 40-week double-blind treatment period, which includes 4 weeks of pretreatment with dupilumab or placebo followed by 24 to 36 weeks of treatment with dupilumab or placebo in combination with a gradual up-dosing of AR101, a 24-week maintenance phase with 300 mg/day AR101 with concomitant dupilumab or matching placebo (for subjects who achieve 300 mg/day AR101 for at least 2 weeks in the up-dosing period), and a 12-week post-treatment follow-up period (Figure 1). Subjects who do not achieve 300 mg/day will still enter the 12-week follow-up. Excluding the screening period, the duration of the study is approximately 64 to 76 weeks for subjects who enter the maintenance period, and 40 to 52 weeks for subjects who do not achieve 300 mg/day AR101 for at least 2 weeks at visit 16 and do not enter the maintenance period.

Figure 1. Schematic of Study Design

Enroll 2-arms (2:1), up-dose AR101 from week 4 to week 28 to 40. Subjects in DUP (dupilumab) +AR101 group will be rerandomized to DUP+AR101 and PBO (placebo) + AR101, but only those subjects who achieve 300 mg/day AR101 for at least 2 weeks will be eligible to enter the 24-week maintenance treatment. Subjects who do not achieve 300 mg/day AR101-CODIT will enter a 12-week follow-up.

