5.7.2. Analysis of Adverse Events of Special Interest

The adverse events of special interest (AESI) for dupilumab and AR101 will be summarized by AESI category (see Section 10.4) and HLT/PT, respectively.

The time to first AESIs (TEAE by category) or TEAE leading to permanent treatment discontinuation will be assessed by Kaplan-Meier estimates. Kaplan-Meier plots will be provided. In order to detect any safety signals, the hazard ratio (HR) will be provided together with the corresponding 95% confidence interval (CI) for the selected adverse events. Hazard ratios will be calculated using a Cox model including factors of treatment group, and randomization strata. The time is defined as the date of first event – the date of first dose + 1. Subjects without an event will be censored at the end of each study period. Graphs of cumulative incidence rate over time will be presented by treatment group.

The number of anaphylactic reactions, the number and percent of subjects experiencing an anaphylactic reaction, the number and percent of subjects experiencing an anaphylactic reaction by maximum severity using the Muraro Grading Scale (Muraro 2007), the number of subjects experiencing an anaphylactic reaction was an SAE, the number of subjects experiencing an anaphylactic reaction that required use of epinephrine will be summarized for each study period and during DBPCFCs.

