6.1. Definition of Baseline for Efficacy/Safety Variables

Unless otherwise specified, the study baseline assessment for all measurements will be the latest available valid measurement taken prior to the first administration of study drug. If any randomized subjects are not treated, the baseline will be the last value on or prior to the randomization. In addition, maintenance period baseline is defined as the last available valid measurement taken prior to the first administration of dupilumab/placebo during the maintenance period.

The following rules specify the determination of baseline by both date/time information:

- The date and time of first injection will be used to determine the baseline for the AE, lab, PK and ADA data.
- Only the date of first injection will be used to determine the baseline for other data expect AE, lab, PK and ADA data.

For the re-screened subjects, all data from the same subject will be used to derive baseline regardless if the data is from the screen-failure subject ID or enrolled subject ID.

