| Visit 22 (Week 52 to 64, V16 + 24 weeks) | Visit 16 TD + 168 days | [Visit 22 TD – 13 days, Visit 22 TD + 14 days] |
| Following window | ws apply to subjects who entered | follow-up period |
| Visit 23 (V16 + 28 weeks) | Target Day (TD) at last visit in pre-dosing/up- dosing/maintenance period ^e + 28 days | [Visit 23 TD – 13 days, Visit 23 TD + 14 days] |
| Visit 24 (V16 + 32 weeks) | Target Day (TD) at last visit in pre-dosing/up- dosing/maintenance period + 56 days | [Visit 24 TD – 13 days, Visit 24 TD + 14 days] |
| Visit 25 (Week 64 to 76, V16 + 36 weeks) | Target Day (TD) at last visit in pre-dosing/up- dosing/maintenance period + 84 days | ≥ Visit 24 TD + 14 days |

^a Study day is calculated relative to the date of first study drug injection.

^b Visit 15a – 15f are optional visits in order to reach 300 mg/day AR101 for at least two weeks. Subjects may reach 300 mg/day AR101 for at least two weeks at any of the optional visits.

^c The last visit during up-dosing period could be any of visit 15, 15a, 15b, 15c, 15d, 15e, or 15f.

^dVisit 16 target day (TD) is defined as target day at last visit during up-dosing period + 14 days.

^e The target day at last visit in pre-dosing/up-dosing/maintenance period could be any of the following visit: 1) visit 15 during up-dosing period; 2) ET visit during up-dosing period; 3) visit 22 during maintenance period; 4) ET visit during maintenance period.

In general, the following order will be used to select the record for analysis at given visit:

- 4. Scheduled visit
- 5. ET or end of study (EOS), whichever comes first if scheduled visit not available
- 6. Unscheduled visit if both scheduled visit and ET/EOT/EOS are not available

For the multiple measurements of the same test in the same window, the following rules will be used to select the analysis value:

- If multiple valid values of a variable within an analysis visit window, the closest from the target study day will be selected.
- If the difference is a tie, the value after the targeted study day will be selected.
- If multiple available values of a variable exist within a same day, then the first value of the day will be selected.

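### Exposure by study period is counted from the first dose of the whole study, so maintenance injection exposure would read 364 to 448 days instead of 168

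*SAP*

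**What the plan says.** SAP 5.5.2 gives two duration formulas, to be presented by treatment group within each study period. For the injections it is "Date of last dupilumab/placebo injection in the respective study period – date of first study drug injection) + 14 days" and for the oral product "Date of last AR101 taken in the respective study period – date of first AR101 taken) + 1 day". The section adds: "These summaries will be provided for each study period separately". In both formulas the period qualifier is attached to the last dose and not to the first.

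SAP 3.3 splits the study into pre-dosing, up-dosing, maintenance and follow-up. Up-dosing opens on the AR101 initial dose escalation day. Maintenance opens the day after the second visit 16 challenge. SAP 2.4 plans "a 24-week maintenance phase with 300 mg/day AR101 with concomitant dupilumab or matching placebo".

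Protocol 11.4.4.3 has the parent formula, for the study as a whole: "Date of last study drug injection – date of first study drug injection) + 14 days".

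SAP 5.7.2, on time to first adverse event of special interest (AESI), says: "The time is defined as the date of first event – the date of first dose + 1". Event-free subjects are censored at the end of each period. The section does not say whether the first dose is that of the study or of the period.

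**The concern.** A table labelled as maintenance exposure should describe dosing in maintenance. As written, the formula gives cumulative exposure up to the end of maintenance. The SAP seems to have taken over the protocol's whole-study formula, made its end date period-specific and left its start date alone.

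SAP 5.7 presents safety by the treatment received in each period, so the exposure tables should cover the same window. The mismatch matters most for subjects re-randomized from dupilumab to placebo. Their maintenance row would include all their earlier time on dupilumab.

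SAP 5.5.1 also computes compliance per period over an exposure period that it does not define. If that window is taken from 5.5.2, maintenance compliance would inherit the same start date.

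**Working it through.** **Which start date is meant.** Three places bear on this.

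- SAP 6.4 uses the same expression for the whole-study clock: "Study day is calculated relative to the date of first study drug injection".
- The observation-period formula, also in SAP 5.5.2, counts from the first study drug injection and is a whole-study measure.
- Where a period-specific first dose is intended, SAP 6.1 says so: "prior to the first administration of dupilumab/placebo during the maintenance period".

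So the literal reading of 5.5.2 is a whole-study start.

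**Inputs.** Injections are every two weeks and the first is on day 1. The initial escalation day is week 4 (day 29). Visit 16 is at week 28 to 40. The visit 16 injection is the first of maintenance (footnote 1 to the maintenance schedule in both documents). Maintenance lasts 24 weeks. Nominal study day = 7 × week + 1.

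**Check on the day convention.** The plan states no maintenance exposure figure. It does give a nominal end of maintenance in SAP 3.3, study day 365, and 52 × 7 + 1 = 365 reproduces it.

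**Nominal dates.**

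- Visit 16 at week 28: last up-dosing injection at week 26 (day 183), first maintenance injection day 197, last at week 50 (day 351), last AR101 dose day 364 (the day before visit 22).
- Visit 16 at week 40: the same points are week 38 (day 267), day 281, week 62 (day 435) and day 448.

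**Results in days.** Injections use last − first + 14; AR101 uses last − first + 1.

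| Period and product | Visit 16 | As written | Start limited to the period |
|---|---|---|---|
| Pre-dosing, injection | either | 15 − 1 + 14 = 28 | 28 |
| Up-dosing, injection | week 28 | 183 − 1 + 14 = 196 | 183 − 29 + 14 = 168 |
| Up-dosing, injection | week 40 | 267 − 1 + 14 = 280 | 267 − 29 + 14 = 252 |
| Maintenance, injection | week 28 | 351 − 1 + 14 = 364 | 351 − 197 + 14 = 168 |
| Maintenance, injection | week 40 | 435 − 1 + 14 = 448 | 435 − 281 + 14 = 168 |
| Maintenance, AR101 | week 28 | 364 − 29 + 1 = 336 | 364 − 197 + 1 = 168 |
| Maintenance, AR101 | week 40 | 448 − 29 + 1 = 420 | 448 − 281 + 1 = 168 |

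Up-dosing AR101 is unaffected, because the first AR101 dose opens that period.

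**Excess in maintenance injection exposure.** 364 − 168 = 196 days (196/364 = 54%) on the 28-week path, and 448 − 168 = 280 days (280/448 = 63%) on the 40-week path.

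**Additivity.** On the 28-week path the three periods as written sum to 28 + 196 + 364 = 588 days, for a subject exposed for 364. With period starts they sum to 28 + 168 + 168 = 364.

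**Time to AESI.** If the first dose in 5.7.2 is that of the study, each subject's maintenance time carries about 196 to 280 days in which no maintenance event can occur. An illustrative Cox simulation assumed a true hazard ratio of 0.5 and 168 days of follow-up. The estimate was 0.533 on the period clock, 0.533 with 196 days added to everyone, and 0.532 with 196 to 280 days added independently of arm. The time axis moves; the hazard ratio hardly does.

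**The case against.** The best defence is that this is an omitted qualifier that any programmer would supply. The duration categories in 5.5.2, which run to 364 days and over, suit a whole-study summary. The section also reports the number of doses, so about 12 maintenance injections (12 × 14 = 168 days) beside 364 days would look odd at once. A drafting slip is indeed likely. But nothing in the SAP limits the formula to a whole-study table or corrects it for a period table, and the wording elsewhere points to the whole-study start.

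On up-dosing, Protocol 11.4.4.1 itself speaks of a 28 to 40 week up-dosing period that takes in the pretreatment, so 196 days agrees with protocol usage. That stands in part. SAP 3.3 does separate the two periods, but the discrepancy is only 28 days, on the same injection.

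A reader might also infer three stronger things, which the documents do not support.

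- *Time is credited to the wrong arm.* No subject's time moves to another group. In the two continuous groups the injection never changes. Only the switched group mixes drugs, and its label in SAP 5 shows the sequence.
- *The AESI hazard ratios are distorted.* The first dose in 5.7.2 is ambiguous rather than plainly that of the study, and a shift common to the arms leaves the ordering of event times, and so the Cox estimate, unchanged. A shift that differed by arm could matter; its effect was not calculated.
- *Adverse event rates have the wrong denominator.* SAP 5.7.1 divides by the number of subjects in the group for the period. It plans no rate per patient-year.

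**Conclusion.** The point holds for the exposure tables. Followed literally, SAP 5.5.2 puts earlier time into the maintenance figures of all three groups, more than doubling injection exposure and at least doubling AR101 exposure. The up-dosing injection figure is too long by the 28 days of pretreatment. For the dupilumab-to-placebo group, the maintenance figure counts 196 to 280 days of dupilumab in a period when placebo is given.

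The day counts assume nominal two-weekly dosing with no missed injections. Visit windows and the interval around the visit 16 challenge would move them by days to a few weeks, which does not alter the conclusion.

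For time to AESI the finding is an undefined time zero. At most it displaces the time axis of the Kaplan-Meier and cumulative-incidence curves. The hazard ratio is not expected to change materially if time to visit 16 is similar between the groups. No efficacy estimate, test decision or adverse event percentage depends on any of this.

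**What to change.** In SAP 5.5.2, attach to the first-dose date in both formulas the same period qualifier that the last-dose date already carries. Keep exposure accumulated from the first dose of the study as a separate overall-study table, where the long duration categories belong.

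In SAP 5.7.2, state that time zero for a period-specific time to AESI is the start of that analysis period as defined in SAP 3.3.

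The cost is a few words in the SAP and the matching lines of the derivation specification. No new data are needed and no efficacy analysis is touched.
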